## Study Information

### Hypotheses

**SPECIFIC AIM 1: Predictors of REDS PRIMARY HYPOTHESES:** H1: Perceived discordance with prior knowledge will predict REDS. We developed an assessment of the degree to which the DA information conflicts with prior knowledge. We predict that when the DA information conflicts with an individuals' prior knowledge about BCS, they will express more disbelief, reactance, self-exemption, and source derogation. H2: Perceived threat and screening efficacy will predict REDS. We derive our predictions from the Extended Parallel Process Model (EPPM) which is an extension of the fear appeal model. The EPPM proposes that people are most likely to reject information when they feel threatened AND feel they cannot do anything to address the threat (i.e. a high threat, low efficacy message). We predict that women who perceive high affective cancer risk AND have high preexisting expectations for screening will express the strongest reactance, self-exemption, disbelief and source derogation (because they experience the DA as a high threat, low efficacy message). We will test this hypothesis by examining pre-test screening expectations (perceived screening benefit minus perceived harm), and pre-test affective cancer risk perceptions, as predictors of "REDS" outcomes. H3: Perceived threat and screening efficacy will predict information rejection after controlling for discordance with prior knowledge. Putting predictors from H1 and H2 together in a model, discordance with prior knowledge will no longer be a significant predictor of REDS whereas affective cancer risk and preexisting expectations of screening will continue to be significant predictors. **SECONDARY HYPOTHESES:** SH1: Other significant predictors of REDS responses will include: 1. stronger injunctive norms (i.e. people think I should screen), 2. Medical maximizing (vs. minimizing), 3. Prior screening use (yes/no), 4. Have friends or family diagnosed with breast cancer (vs. not), 5. Lower pre-test trust in the healthcare system, 6. Viewing screening as a protected value (i.e. moral imperative). We predict that all of these variables will show significant bivariate correlations with REDS responses but we do not have specific hypotheses about which will be significant in a model including all predictors. SH2: Relative to White women, Black women will express more self-exemption (feeling that the information does not apply to them) but not necessarily more disbelief, reactance or source derogation. Our rationale for using race as a predictor is that, due to longstanding health disparities related to insufficient care among minority women, and a historic lack of inclusion of BIPOC individuals in clinical trials, Black women will be more likely than White women to believe that the information does not apply to them. SH3: Factors that will not significantly predict REDS will include: 1. Insurance status, 2. Structural barriers, 3. Pre-test knowledge. **SPECIFIC AIM 2: Predictors of screening intentions** H4: There will be an association between objective cancer risk and screening intentions such that women at higher cancer risk will be more likely to intend to screen before 50 (vs. wait to screen or not screen at all). H4a: There will also be an interaction such that women with lower REDS responses will show a stronger correlation between objective cancer risk and screening intentions, and women with higher REDS will show smaller or null correlations between objective risk and intentions. H5: There will be an association between post-DA knowledge and

screening intentions such that women with lower post-DA knowledge will be more likely to intend to screen before 50. H5a: There will also be an interaction with REDS such that women with lower REDS responses will have a stronger correlation between knowledge and intentions, and women with stronger REDS will show smaller or null correlation between knowledge and screening intentions. Other secondary hypotheses related to the effect of the DA and the nature of REDS: SH4: Trust in the healthcare system will decrease from pre- to post-DA. This effect will be stronger for women with greater REDS responses. SH5: Screening knowledge will improve from pre- to post-DA. REDS responses will be associated with less knowledge increase from pre to post-DA, and will be associated with less total knowledge post-DA. SH6: Perceived screening benefits will decrease from pre- to post-DA; perceived screening harms will increase. REDS responses will be associated with less change from pre- to post-DA. SH7: REDS are predicted to reflect a more emotion-laden set of reactions, whereas perceived discordance with prior knowledge is conceptualized as a more cognitive reaction. Therefore, REDS will be associated with emotional responses to the DA (anger, anxiety), whereas perceived discordance with prior knowledge will not be associated with emotional responses to the DA (after adjusting for REDS).

## Design Plan

### Study type

Observational Study - Data is collected from study subjects that are not randomly assigned to a treatment. This includes surveys, “natural experiments,” and regression discontinuity designs.

### Blinding

- No blinding is involved in this study.

Is there any additional blinding in this study?

No additional blinding.

### Study design

Cross-sectional survey

*No files selected*

### Randomization

No randomization was performed (observational study).

## Sampling Plan

### Existing Data

Registration prior to analysis of the data

Explanation of existing data

There is no previously existing data. Weekly summary reports will be generated as data is collected to check for data collection issues and to identify eligible individuals for qualitative studies. No inferential statistics will be computed with these data.

### Data collection procedures

Participants will be recruited through Ipsos.

*No files selected*

Sample size

Our expected sample size is 500 participants.

Sample size rationale

The study was powered to detect an interaction between objective cancer risk and REDS on receipt of screening (Aim 2). We estimated power by simulation based on 2000 data sets using R statistical software. We use a logistic regression model for the outcome of screening (yes/no) with fixed effects for REDS (high/low) and objective cancer risk (continuous) and their interaction. Assuming that there is a probability of 50% of high REDS (treated as a binary variable), a sample size of 500, and that 10% of variability is explained by other factors in the model (confounders), we would be able to detect a difference in the log odds of -0.3 with 90% power (alpha=0.05). Thus, if the odds of the outcome is 1 in the low REDS group, for every unit increase in cancer risk we can detect an odds of 0.74 (=exp(0-0.3)) in the high REDS group (i.e., an odds ratio of 1.35). Additionally for the outcomes in Aim 1, with a sample size of N=500 we will be able to estimate the prevalence of REDS with a margin of error of 2.8-3.0% depending on the actual prevalence 30-70%. The sample size of 500 will also allow us to detect an increment of 1.2% in variability explained in the linear regression models assuming other factors explain 20% of the variability with 80% power (alpha=0.05).

Stopping rule

We have contracted with Ipsos to collect 500 participants.

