AIM 1: Identify the prevalence and predictors of REDS in reaction to evidence about mammography benefits and harms, and consequences for decision-making and trust. Research has not yet systematically identified the proportion of women who respond negatively (vs. positively) to mammography evidence, or attempted to explain these responses by examining theory-driven predictors. We will develop and conduct a probability-based nationally representative survey in which we communicate mammography evidence using the current best practices in risk communication, and identify theory-driven predictors of REDS responses, and identify consequences of these responses for decision-making and trust.

II. Background and Significance:

A1. Screening recommendations have changed considerably over recent years.

Breast cancer is the second leading cause of cancer death among women in the U.S., and early detection can result in a cure before it spreads. For many years mammography was strongly promoted, with the aim of maximizing screening uptake.¹⁰⁻¹² However, mammography guidelines have changed considerably as a result of accumulating evidence showing that screening has less benefit for some populations of women, and can cause harm.¹³⁻¹⁵ Harms include false positive results requiring follow-up tests and biopsies, and overdiagnosis—the diagnosis of asymptomatic cancer that will not cause symptoms or harm in a person's lifetime—and resultant overtreatment.¹⁶⁻¹⁸ Although routine mammography is still strongly recommended for women in specific age ranges

and with certain risk factors, many expert groups, including the United States Preventive Services Task Force (USPSTF) and the American Cancer Society (ACS), have de-intensified screening recommendations and expanded the role of informed choice.^{2,4} Most guidelines now emphasize that women should receive balanced information about the benefits and harms of mammography so that they can engage in shared decision making (SDM) and make an informed choice with their doctor about when to start, when to stop, and how frequently to screen.¹⁹

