B. Description of Population to be Enrolled:

Inclusion:

- Female
- Between 39-49 years of age
- No history of breast cancer
- No known BRCA1/2 mutation

Exclusion:

- Non-English or Spanish Speaking
- Persons unable to provide informed consent (e.g. severe dementia or cognitive disability or illiterate)
- History of breast cancer
- Known BRCA1/2 mutation

Pilot Survey: We will pilot test questions to measure REDS and cognitive reactions to assess item variability, internal consistency, and reduce the total number of items. We will recruit 700 women through Dynata. Dynata manages an online participant panel of millions of adults across the United States. Participants who are part of Dynata's panel have agreed to participate in surveys in exchange entry into lotteries for small cash prizes.

Pilot Interviews: We will recruit up to 15 women from [name]'s Internal Medicine clinic at UCHealth. These interviews will focus on assessing overall knowledge and understanding of the information presented in the decision aid. Participants will receive a \$25 gift card for participating in the interview.

Nationally Representative Survey: We will recruit 700 women age 40-49 through Ipsos Public Affairs. Ipsos manages an online participant panel allowing population inferences using probability sampling methods and providing Internet access to households that do not have it.

Nationally Representative Interviews: We will recruit up to 40 women from the Ipsos survey who agreed to be contact for a follow-up phone interview. We will specifically recruit women who expressed negative reactions to mammography evidence, so that we can assess how to improve the BCS-DA using insights from those who were negatively affected. We will attempt to recruit at least 25% non-White participants for these interviews.

C. Study Design and Research Methods

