The length of the survey may be an issue since we are recruiting through Ipsos.

There is a possibility that not a sufficient amount of subjects with voluntarily self-identify for the follow-up interviews.

F. Data Analysis Plan:

Pilot Survey: We will check the variability of each questionnaire item to assess suitability for exploratory factor analysis. Exploratory factor analysis will be used to identify the factor structure of the REDS items. Items that do not load onto any factor will be dropped. Reliability of the remaining items

Nationally Representative Survey: Summary statistics will estimate the prevalence of REDS to each part of the BCS-DA. Simple within-subjects tests (e.g. ANOVA) will compare REDS in response to screening benefits, false positives, and overdiagnosis.

All Interviews: We will conduct exploratory content analysis of these qualitative interviews using the analytic program Dedoose to extract themes in patients' reactions to the presented information.

Safety Oversight:

The principal investigator will be responsible for the conduct of this study, overseeing participant safety, executing the data and safety monitoring (DSM) plan, and complying with all reporting requirements to local and federal authorities. This oversight will be accomplished through additional oversight from the Data and Safety Monitoring Committee (DSMC) at the University of Colorado Cancer Center (CU Cancer Center). The DSMC is responsible for ensuring data quality and study participant safety for all trials at the CU Cancer Center. A summary of the DSMC's relevant activities is as follows:

- Conduct of internal audits

- Has the authority to suspend studies for safety or conduct issues
- May submit recommendations for corrective actions to the CU Cancer Center's Executive Committee

Study audits conducted by the DSMC will consist of a review of the regulatory documents, consent forms, and source data verification. Documentation of the audit conducted by the DSMC will then need to be submitted to the IRB of record at the time of the IRB's continuing review of this trial (if applicable).

G. Summarize Knowledge to be Gained:

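### The stated margin of error for REDS prevalence (2.8-3.0% at N=500) does not reproduce; at 95% confidence it is 4.0-4.4%

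*SAP*

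**What the plan says.** The SAP, under Data collection procedures, sets the sample size: "Our expected sample size is 500 participants". The sample size rationale there first describes a simulation for the Aim 2 interaction. It then says of Aim 1 that at N=500 "we will be able to estimate the prevalence of REDS with a margin of error of 2.8-3.0% depending on the actual prevalence 30-70"%. No confidence level, formula or design effect accompanies this margin. The next sentence gives a second Aim 1 figure, a detectable increment of 1.2% in explained variability over 20% from other factors, with 80% power and alpha 0.05.

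Prevalence is a named target. Protocol section I puts it first in Aim 1, and section IV.F (Data Analysis Plan) says: "Summary statistics will estimate the prevalence of REDS to each part of the BCS-DA". Section I also calls the survey probability-based and nationally representative.

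**The concern.** The sentence supplies both N and the prevalence range, so the margin can be checked directly once a confidence level is chosen. At the conventional 95% level, a proportion near one half estimated from 500 people has a margin of a little over 4 points, not 3.

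This is the only precision figure the documents give for REDS prevalence. Taking the margin as a 95% half-width, a reader would expect an interval 5.6 to 6.0 points wide (2 × 2.8 to 2 × 3.0). The calculation gives 8.0 to 8.8 points (2 × 4.02 to 2 × 4.38). The discrepancy flatters the study.

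**Working it through.** **Inputs.** N = 500, prevalence p from 0.30 to 0.70 and a margin of 2.8-3.0% all come from the SAP sentence. The 95% level is an assumption. Its support is that alpha 0.05 is the only error level in the sample size rationale, and the SAP's Inference criteria use p < 0.05.

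**Attempt to reproduce the figure.** Margin = z × sqrt(p(1−p)/N).

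- p = 0.30 or 0.70: standard error = sqrt(0.21/500) = 2.049%; × 1.96 = 4.02%.
- p = 0.50: standard error = sqrt(0.25/500) = 2.236%; × 1.96 = 4.38%.

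The stated 2.8-3.0% is not recovered.

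**Size of the gap at 95%.**

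- Lower end: 4.02/2.8 = 1.43; shortfall 1 − 2.8/4.02 = 30%.
- Upper end: 4.38/3.0 = 1.46; shortfall 1 − 3.0/4.38 = 32%.

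**Other settings, to see whether any gives 2.8-3.0%.**

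| Setting | Margin at p = 0.30 | Margin at p = 0.50 |
|---|---|---|
| N=500, 95%, Wilson | 4.00% | 4.37% |
| N=500, 95%, Agresti-Coull | 4.01% | 4.37% |
| N=500, 95%, Jeffreys | 4.01% | 4.37% |
| N=500, 95%, exact | 4.11% | 4.47% |
| N=500, 90% | 3.37% | 3.68% |
| N=500, 85% | 2.95% | 3.22% |
| N=500, 80% | 2.63% | 2.87% |
| N=700, 95% | 3.39% | 3.70% |
| N=700, 90% | 2.85% | 3.11% |
| N=1,000, 95% | 2.84% | 3.10% |

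None gives the stated pair. N=700 was tried because Protocol section IV.B plans that number for the Ipsos survey ("We will recruit 700 women age 40-49 through Ipsos Public Affairs"). It comes near only at 90%, and the SAP sentence specifies 500.

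**What the stated figure would require.**

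- At N=500: z = 2.8/2.049 = 1.366 (82.8% confidence) and z = 3.0/2.236 = 1.342 (82.0% confidence).
- At 95%: N = 1.96² × 0.21/0.028² ≈ 1,029 and N = 1.96² × 0.25/0.030² ≈ 1,067.

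**Cross-check on the neighbouring sentence.** Assume an F test with 1 degree of freedom, which the SAP does not specify. For an increment of 0.012 over an R² of 0.20, f² = 0.012/(1 − 0.20 − 0.012) = 0.0152. At N=500 and alpha 0.05 the power is 78.6%. The smallest increment detectable with 80% power is 1.24%, against 1.2% stated; at N=700 it would be 0.89%. On that reading the neighbouring figure rests on N=500 and a 5% level, and the margin is the figure that does not fit.

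**Design effect.** All the margins above assume simple random sampling. With a design effect D the margin is multiplied by sqrt(D). The documents give no D. For illustration, D = 1.5 turns 4.0-4.4% into 4.9-5.4%.

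**The case against.** The arithmetic is not in dispute; the case on the other side concerns how much can be inferred from it.

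1. **The confidence level is unstated.** The 4.0-4.4% figure is therefore conditional on 95%, and alpha for a power calculation does not fix the level of a descriptive interval. This stands as a condition. It does not rescue the sentence, since none of the usual levels gives 2.8-3.0% at N=500 and a margin without its level cannot be interpreted.
2. **The cross-check depends on a 1-degree-of-freedom test.** With 2 or 3 degrees of freedom, power for the same increment falls to 69.2% or 62.6%, and the analysis for H3 describes adding a set of predictors. This also stands: the cross-check makes N=500 and a 5% level plausible but does not prove them. The main calculation does not need it.
3. **Pooling three domain responses per woman could come out at the stated range.** With 1,500 responses and an intraclass correlation of 0.21, the effective N is 1,500/(1 + 2 × 0.21) ≈ 1,056, giving 2.76-3.02%. The documents describe no such calculation, and Protocol section IV.F estimates prevalence separately for each part of the decision aid. The SAP would collapse domains only when correlations exceed 0.50; at an intraclass correlation of 0.50, pooling gives 3.28-3.58%.
4. **The practical effect is small.** The final interval will be computed from the data, the SAP's models treat REDS as continuous, and N does not depend on this figure. That is right and limits the weight of the point. It does not make the stated number correct.

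**Conclusion.** The concern holds. The SAP's 2.8-3.0% margin cannot be reproduced from its own N and prevalence range at any usual confidence level. At 95% under simple random sampling the margin is 4.0-4.4%, which is 43-46% wider than stated. The 95% level is an assumption, consistent with the 5% level used elsewhere in the SAP. Any design effect above 1 would widen the margin further.

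The error affects only the stated precision of the Aim 1 prevalence estimate. It does not touch the Aim 2 power calculation that set the sample size, the models, or any listed hypothesis test. It should be fixed because prevalence is a named aim and this is its only precision statement.

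**What to change.** In the SAP's sample size rationale, replace 2.8-3.0% with 4.0-4.4%, labelled as a 95% confidence half-width at N=500 under simple random sampling, before any design effect. If panel weights will be used for the national prevalence estimate, add the assumed design effect and multiply the margin by its square root.

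If another level or method was intended, state it and give the figure that follows from it; at 90%, for example, this is 3.4-3.7%.

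The cost is one sentence in the SAP. Enrolment, models and tests are unchanged, and the stated precision becomes less favourable.

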## Variables

Manipulated variables

Not applicable (observational study)

*No files selected*

Measured variables

Reaction to screening benefits: Reactance (4 items), Self-exemption (4 items), Disbelief (4 items)

Reactions to overdiagnosis: Reactance (4 items), Self-exemption (4 items), Disbelief (4 items)

Reactions to false positives: Reactance (4 items), Self-exemption (4 items), Disbelief (4 items)

Bayesian updating (4 items) – asked three times for the three domains (benefits, overdiagnosis, false positives) Source trust/derogation in reaction to DA as a whole – 4 items Each of the items indicated above are Likert scale questions Screening intentions: categorical outcome (screen before 50, wait to screen until 50, never intend to screen) Screening knowledge (Hersch et al 2015) – add up number of questions or proportion correct (pre-DA and post-DA)

*No files selected*

Indices

We will compute Cronbach's alpha reliability for the REDS items to justify collapsing them into a single measure (mean of all items). We will compute correlations among the REDS scores (10 scores: source derogation to decision aid (DA) as a whole; reactance, self-exemption, and disbelief for benefit, overdiagnosis, false-positives). If responses across the three domains are highly correlated ( $r>0.50$ ), and the Cronbach's alpha among the individual items is also high

(alpha>0.70) then we will further reduce the data by collapsing across the domains to obtain a mean score. This would result in a single score for each REDS construct (4 total scores). Otherwise, if responses are moderately correlated we will use multivariate analyses to test hypotheses, and if responses has low correlation we will test hypotheses below separately for reactions to benefits, overdiagnosis, and false-positives.

*No files selected*

## Analysis Plan

Statistical models

H1. Perceived discordance with prior knowledge will predict REDS. • Dependent variable: Overall score averaged across REDS domains [Continuous] • Independent variable: Bayesian updating (4 items) averaged [Continuous] • Hypothesis: Higher (more negative) scores on conflicts with prior knowledge (Bayesian updating) will be correlated with higher (more negative) scores for other domains • Hypothesis: Higher correlation for the benefits domain than the other two domains (overdiagnosis and false positives) • Analysis: Compute bivariate correlation between these two scores within each informational domain; No plans to adjust for covariates in this analysis. Fit linear regression model (correlation) for association between Bayesian updating and REDS. H2. Perceived threat and screening efficacy will predict REDS • Dependent variable: Overall REDS [Continuous] • Independent variable: Pre-test perceived threat (average of 3 affective risk questions; should have high reliability) [Continuous] • Independent variable: Pre-test screening efficacy (questions on how beneficial and harmful is screening) = (perceived benefit – perceived harm) [Continuous] • Hypothesis: Women who perceive high affective cancer risk AND have high preexisting expectations for screening will express strongest (most negative) REDS • Analysis: Linear regression model for overall REDS with interaction term between perceived threat and efficacy (interaction effect indicates that the effect of perceived threat on REDS is modified by screening efficacy) • Interpretation/Visualization: Will make at least one of the variables binary H3. Perceived threat and screening efficacy will predict information rejection after controlling for discordance with prior knowledge (Bayesian updating). • Dependent variable: Overall REDS [Continuous] • Independent variable: Perceived threat (average of 3 affective risk questions) [Continuous] • Independent variable: Screening efficacy (perceived benefit – perceived harm) [Continuous] • Independent variable: Bayesian updating (4 item) [Continuous] • Hypothesis: Contribution of Bayesian updating will be less than the emotional factors • Analysis: In regression model for H2, adjust for Bayesian updating and assess interaction effect and effect of Bayesian updating. Compare to models H1 and H2 and assess whether fit (total variance explained; R-squared) is improved (change in variance when you add the second set of predictors). Perform analysis for each of the domains and see if results are consistent across the domains. SH1: Other significant predictors of REDS • Predictors: 1. stronger injunctive norms (i.e. people think I should screen), 2. Medical maximizing (vs. minimizing), 3. Prior screening use (yes/no), 4. Have friends or family diagnosed with breast cancer (vs. not), 5. Lower pre-test trust in the healthcare system, 6. Viewing screening as a protected value (i.e. moral imperative), 7. Structural barriers, 8. Pre-test knowledge • Analysis: Perform bivariate analyses to assess for the association between the predictors and the REDS. We will also add these variables to the H3 models, to test the unique

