Altogether, the weight of the evidence suggests that communicating mammography screening evidence can elicit negative reactions. The types of negative reactions that we are particularly concerned about include **Reactance** (i.e. perceived manipulation or influence, e.g. "this is trying to ration healthcare"), **self-Exemption** (e.g., "this doesn't apply to me"), **Disbelief** (e.g., "you can't believe all the research anyway"), and **Source derogation** (e.g., "I don't trust this source"), which we shorten to **REDS**.^{8,9} These responses are sometimes referred to collectively as "defensive coping",³⁶ although we prefer "REDS" to refer directly to the four types of responses. To date, no research has examined REDS systematically to assess their prevalence and causes in the context of communicating mammography screening evidence. And even though many women

react negatively to screening information, many women also want to be informed and be able to make a choice.³⁷ The result is a delicate situation in which there is need to convey the evidence to women, but also a need to do it in a way that maintains credibility and trust.

III. Preliminary Studies/Progress Report:

IV. Research Methods

A. Outcome Measure(s):

The primary outcome measures in this survey are REDS responses and screening intentions. See Table 1 below for all survey measures.^{35,55,56,61,66,72,96-99}

	Measure description	Source
Primary DVs	REDS responses	See appendix
	Screening intentions	Schapira et al. 2019
Secondary DVs	Change in trust in provider and healthcare system, pre vs. post BCS-DA	Egede et al. 2008
	Positive responses, e.g. appreciation of information	Ad hoc
	Change in screening knowledge, pre vs. post BCS-DA	Schapira et al. 2019
IVs: primary	Breast cancer risk perceptions: affective, deliberative, experiential	Ferrer et al. 2016
	Perception of net screening benefit (benefits minus harms) at pre-test	[name] et al., 2018
	Objective breast cancer risk	Schapira et al. 2019
	Cognitive responses to information	See appendix
	Medical Maximizing-Minimizing orientation	[name] et al., 2016
	Perceived norms	Hersch et al., 2015
	Past screening experience	Petrova et al., 2015
Secondary IVs and control variables	Perceived barriers to screening	Hyman & Baker 1992
	Friends/family experience with breast cancer	Petrova et al., 2015
	Subjective numeracy	Fagerlin et al., 2007
	Health literacy	Chew et al., 2008
	Demographics	Standard questions

Table 1. Aim 1 measures.

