The survey flow is displayed in the figure below and will unfold as follows: First, women will be asked premeasure questions displayed in the figure below. Second, women will learn their objective cancer risk estimate, and will report their affective, deliberative and experiential risk perceptions.⁵⁶ Third, women will react separately to the three distinct components of mammography evidence (benefits, false positives, overdiagnosis). The purpose of assessing reactions to each component of the evidence is to identify how positively or negatively each part is received. We anticipate that overdiagnosis may be received most negatively. Measured reactions will include REDS responses, and cognitive reactions as previously described (i.e. whether the information is compatible or not with other knowledge). Finally, after all of the information has been presented, women will provide overall reactions to the evidence using the same measures. Next women will report overall positive responses, e.g., the extent to which they appreciated receiving the information, felt empowered by it, and

want to talk to their provider about it. Lastly, women will repeat some of the pre-measures (e.g. knowledge, trust) and report demographics and individual differences.

Pilot Survey: Recruitment and survey distribution will be done by Dynata. All data will be collected electronically using Qualtrics.

Nationally Representation Survey: Recruitment and survey distribution will be done by Ipsos. All data will be collected electronically using Qualtrics.

All Interviews: Patients will be invited to schedule a phone call for the interview (using a regular phone or using Zoom), and audio will be recorded and transcribed.

D. Description, Risks and Justification of Procedures and Data Collection Tools:

Benefit from participating in the research cannot be claimed. Women will learn about mammography benefit and harm, which may lead to more informed screening decisions. Learning how to help communicate more effectively about counterintuitive and surprising medical evidence is an area in great need of attention. The intervention is designed to improve communication and decision quality and enhance the overall decision making. Given that the risks are minimal and the benefits great (to both patients, clinicians, and society as a whole) we believe that the benefits of the proposed project outweigh any risks.

E. Potential Scientific Problems:

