#### *No files selected*

#### Transformations

The REDS components and Bayesian updating scores will be computed by averaging across the Likert scale questions. The overall REDS score will be averaged across the REDS domains. Additional averaging across the settings of screening benefits, overdiagnosis, and false positives will be performed if there is strong correlation. Perceived threat will be an average of the three affective risk questions. Pre-test screening efficacy will be computed as (Perceived benefit - Perceived harm).

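### H3 treats the affective-risk main effect as emotional, but no SAP model adjusts for the deliberative and experiential risk perceptions that the protocol also collects

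*SAP*

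**What the plan says.** Protocol section IV.A, Table 1, lists among the primary independent variables "Breast cancer risk perceptions: affective, deliberative, experiential". Protocol section IV.C places them after women see their objective risk estimate and before the mammography evidence; women "will report their affective, deliberative and experiential risk perceptions".

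The SAP narrows this to one component. Under Analysis Plan, H2 defines threat as "Pre-test perceived threat (average of 3 affective risk questions; should have high reliability", H3 repeats "Independent variable: Perceived threat (average of 3 affective risk questions) [Continuous", and Transformations confirms that "Perceived threat will be an average of the three affective risk questions". The Hypotheses section takes the choice of affective risk from the Extended Parallel Process Model (EPPM).

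The other two components enter no SAP model. They are not in H2 or H3, and they are not among the eight SH1 predictors, of which the plan says "We will also add these variables to the H3 models, to test the unique" contribution of each. They are not in SH3 either. Objective risk appears only in H4 and H4a.

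H3 also carries an interpretation: "Contribution of Bayesian updating will be less than the emotional factors". The Hypotheses section adds that discordance should lose significance in the joint model while affective risk and screening expectations keep theirs.

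**The concern.** A woman who thinks breast cancer is likely for her will often also feel worried about it. If the model contains only the feeling, its coefficient picks up whatever part of the belief is correlated with it. The only cognitive competitor in H3 is Bayesian updating, which asks whether the decision aid conflicts with what she already knew. It does not ask how likely she thinks cancer is.

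A belief about likelihood that drives REDS could therefore appear as a significant affective term and be reported as emotional. The same holds for the R-squared gain that H3 credits to the threat and efficacy block. What is at stake is the label on the H3 result, and any later choice between addressing feelings and addressing risk beliefs when the decision aid is revised.

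**Working it through.** **1. The plan's own figure.** The SAP's Sample size rationale gives N=500, other factors explaining 20%, alpha 0.05, and 80% power for a 1.2% increment. Using the noncentral F test with 1 numerator df, f² = ΔR²/(1 − R²other − ΔR²) = 0.012/(1 − 0.20 − 0.012) = 0.01523, and λ = N·f² = 7.61. Power is 78.6%. An increment of 1.24% gives exactly 80%, so the stated figure reproduces.

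**2. Affective main effect when the other components are left out.** *Assumptions, not in the documents:* the true affective effect is zero, deliberative risk has standardised slope b, and the three components correlate pairwise at r. The affective term then takes an apparent slope of about r·b and an apparent ΔR² of (r·b)². For b = 0.2:

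| r | r·b | ΔR² | λ | P(p<0.05), formula | simulation, planned model |
|---|---|---|---|---|---|
| 0.3 | 0.06 | 0.0036 | 2.26 | 32% | 31% |
| 0.5 | 0.10 | 0.0100 | 6.33 | 71% | 68% |
| 0.7 | 0.14 | 0.0196 | 12.56 | 94% | 93% |

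The simulation used 4,000 data sets per row and a model with affective risk, efficacy and their product. Adding the two omitted scales brings the rate to about 5% in every row. With b = 0.25, and depending on what is assumed about efficacy, the planned model gives 34% at r = 0.3, 74% to 80% at r = 0.5, and 95% to 97% at r = 0.7. The overall range is therefore roughly 31% to 97%.

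**3. The threat-by-efficacy interaction.** This is the test that H2 names.
- If deliberative risk acts only as a main effect, the affective-by-efficacy term is significant in about 5% of samples, which is nominal.
- If deliberative risk also interacts with efficacy (assumed slope 0.15 to 0.2, r = 0.3 to 0.7), the affective-by-efficacy term is falsely significant in about 20% to 92% of samples.
- In that second case, adding the other components as main effects alone leaves the 20% to 92% unchanged. Adding their products with efficacy restores about 5%.

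**4. Cost of adjustment.** If the other two scales explain a share R² of affective variance, a 1.2% increment shrinks to a unique 1.2% × (1 − R²). At N=500:

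| R² of affective risk on the others | unique ΔR² | power | N for 80% |
|---|---|---|---|
| 10% | 1.08% | 74% | 575 |
| 25% | 0.90% | 66% | 692 |
| 40% | 0.72% | 57% | 866 |
| 50% | 0.60% | 49% | 1,041 |
| 60% | 0.48% | 41% | 1,302 |

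With equal pairwise correlations, R² = 2r²/(1+r). That is 0.18/1.3 = 14% at r = 0.3 and 0.98/1.7 = 58% at r = 0.7, so the range in step 2 falls within this table.

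**The case against.** The best defence is that affective risk was chosen on purpose. H2 comes from a fear-appeal theory, the measure is fixed in advance, and the claim is one of prediction in a cross-sectional survey. Leaving a collected subscale out of a model is not in itself an error. This stands for H2.

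A reader might infer that the main Aim 1 conclusion, emotion rather than cognition, is invalid. The documents do not go that far. H2 and H3 are titled in terms of perceived threat and screening efficacy. The emotional label appears once in the H3 model description, and it covers efficacy as well, which is benefit minus harm and so itself a belief. H3's comparator is one specific construct, discordance, and that is in the model. SH7's contrast of emotion with cognition does not use risk perception. What remains is narrower: H3 predicts that affective risk stays significant and calls it emotional, and nothing in the model supports that word.

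A reader might also carry the 31% to 97% over to H2's interaction. That does not follow: the interaction keeps its nominal rate unless another risk component also interacts with efficacy.

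Nor do the documents show that the other items were dropped from the survey. The SAP's Measured variables list names no risk-perception items, not even the affective ones, so it settles nothing either way.

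Finally, the correlations and slopes are assumed, and the adjusted fit loses power. Both points stand. The second argues against any rule that removes the affective label whenever the adjusted term is non-significant.

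**Conclusion.** The point holds in a limited form. Two of three protocol-listed primary risk components appear in no SAP model, so H3 cannot attribute the affective main effect to emotion rather than to correlated beliefs about risk. The limit lies in the planned models. If all three components were fielded, the data can address it.

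The 31% to 97% depends on a zero true affective effect, a deliberative slope of 0.2 to 0.25 and correlations of 0.3 to 0.7, none of which the documents supply. It illustrates how large the problem could be and does not estimate this study's error rate. The planned tests remain valid as tests of prediction. The change is worth making because it limits what H3 may conclude and should need no new data.

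**What to change.** Confirm that the deliberative and experiential items were fielded as protocol section IV.C describes. If so:

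- Keep the planned H2 and H3 models as primary.
- Pre-specify companion fits that add deliberative and experiential risk **and** their products with screening efficacy. Centre the predictors, so that the affective main effect is read at average efficacy.
- Report the affective estimates and confidence intervals from both fits side by side.
- State beforehand what counts as material shrinkage. If the affective terms shrink by that much, describe the result as perceived risk, or as not distinguishable from perceived risk, and not as emotional.
- Do not read a non-significant adjusted term as absence of an emotional effect.

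The cost is four extra terms per model and lower precision in the companion fit. Power for a 1.2% affective increment falls from about 79% to 66% if the other scales explain 25% of affective variance, and to 49% at 50%. For that reason the fit should accompany the planned model and not replace it. If the items were not fielded, the only remedy is to drop the emotional label from H3.
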